The transmission potential of SARS-CoV-2 is determined in any particular context by the basic reproduction number ( $R_0$ ) when there is no protective immunity in the population.  $R_0$  will vary with time and context, such as population density, number of contacts and environmental conditions, and is dependent on the period of infectiousness, viral load, and the serial interval. Early data estimated the  $R_0$  for SARS-CoV-2 between 2.0 and 3.4 (Ferretti 2020; Li 2020), higher than that for seasonal influenza (Biggerstaff et al 2014). This is likely in part because of key divergent features from influenza such as pre and asymptomatic SARS-CoV-2 transmission (Ferretti 2020; Kimball 2020; He 2020), near absence of severe disease in young children (Wu et al 2020), and a longer estimated serial interval of 3.96 days (Du Z Emerging Infect Dis 2020). The SARS-CoV-2 average  $R_0$  is also higher than estimated for previous novel viruses, such as influenza H1N1 in the 1918 ( $R_0=1.8$ ) and 2009 ( $R_0=1.6$ ) pandemics (Biggerstaff et al 2014) and SARS-CoV-1 ( $R_0=1-5$ ) (Liu et al 2020).

To date, evidence suggests that in temperate climates between 20 and 50% of infections could be asymptomatic (Mizumoto et al 2020; Bi et al 2020; Kimball et al 2020). Pre-symptomatic shedding is common, with comparable viral load in asymptomatic, pre-symptomatic and clinical cases (Kimball et al 2020). This complicates timely targeted application of interventions since people may not know they are infected and will not behave as if they were. The frequency of asymptomatic infection in sub-Saharan African settings is as of yet unclear, and also may vary by setting. Understanding the proportion of asymptomatic infections and their contribution to the reproduction number is important.

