## 1.2 Rationale

It is recognized that SARS-CoV-2 will transmit differently in African settings, and that risk factors for infection and mild or severe disease may be different to higher income settings. Understanding transmission and identifying at-risk populations is urgent for African countries, who need to target scarce resources as effectively as possible to interrupt transmission and protect vulnerable risk groups.

Box. The epidemiological situation in Mozambique on 29/09/2020.

The SARS-CoV-2 outbreak is still accelerating in Mozambique, as indicated by both the trend in the number of reported cases and the positivity rate. 7983 SARS-CoV-2 infected cases were reported, including 295 imported cases, and 58 deaths. Since the start of the outbreak, 134,011 suspected cases have been tested. In September 2020, consistently more than half of new cases were reported in Maputo City. In Maputo City a total of 3,427 cases and 38 deaths have been reported. The average number of new daily cases reported went from 47 in the first week of September, to 97 in the week up to 26/09. A sero-prevalence survey undertaken in the last two weeks of August 2020, found an overall seroprevalence of 3.8% in Mauto city, with only slight variation between age groups (range 3.0% in 35-59 year olds to 4.5% in  $\geq 60$  year olds). Nevertheless, the latter age group accounts for the majority of hospitalisations. Of all cases reported in Mozambique, 56% were asymptomatic, 37% have a mild symptomatology, 6% moderate symptomatology and 1% a severe symptomatology. 42% of the infected individuals are female.

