An **age-stratified random sample** of that population will be selected for the **repeated sero- and social mixing survey**. By age stratum (0-17 years; 18-50 years; >50 years) we randomly select 800 individuals (simple random sample per age stratum; 2400 in total) from the Polana Caniço HDSS population (regardless of infection or disease status or history), from whom during home visits dried blood spots will repeatedly be collected at 0, 3, 6 and 12 months, vaccination status against COVID-19 will be recorded, and who will be asked to respond to a social mixing questionnaire. A HDSS sampling frame of all individual participants in the HDSS with socio-demographic data and unique identifiers, is available, and will be used to select a simple random sample of individuals by age group.

When a member of a household with no prior widespread transmission (see exclusion criteria) tests SARS-CoV-2 positive, we will revisit the household twice for a household transmission investigation: as soon as possible after the result of the household index case (baseline), and once again one month after symptom onset of the household index case. An initial contact report form will be filled in as soon as possible, ideally within 24 hours, after laboratory confirmation of the primary case in the household. Respiratory and dried blood spot samples will be collected of everyone considered resident (as defined by the HDSS) in the household and who has been in contact with the SARS-CoV-2 positive individual, regardless of age and presence or absence of symptoms. Respiratory samples will be analysed by RT-PCR for SARS-CoV-2 to assess presence of virus and viral load. The dried blood spots for serology on the Luminex assay. Data will be collected on household exposures of contacts and vaccine receipt. Symptomatic household contacts will be tested whenever symptoms appear, as part of the population-based surveillance. This is planned for upto 100 household index cases.

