### 5. Study Procedures

#### 5.1 Study/visit schedule

Table 2. Schedule of assessments for population-based surveillance. One row corresponds to two weeks.

we ek	month	Informed consent (1)	Sero- survey	Household visit (2)	Unscheduled visit for swab collection	Case Follow- up outcome (3)	Social mixing & uptake (4)
1	Oct20	x	x	x		x	
3				x	x	x	
5	nov/20			x	x	x	x
7				x	x	x	
9				x	x	x	

11	dec/20			x	x	x	
13			x	x	x	x	
15	jan/21			x	x	x	
17				x	x	x	x
19	feb/21			x	x	x	
21				x	x	x	
23	mar21			x	x	x	
25			x	x	x	x	x
27	apr/21			x	x	x	
29				x	x	x	
31	may21			x	x	x	
33				x	x	x	
35				x	x	x	
37	jun/21			x	x	x	
39				x	x	x	
41	jul/21			x	x	x	
43				x	x	x	
45	aug/21			x	x	x	
47				x	x	x	
49	sep/21			x	x	x	x
51			x	x	x	x	
53						x	
55						x	
TOTAL forms filled*		2800 for household surveillance,2400 for sero-survey,8000 for swab collection	2400*4= 9600	2800*5= 70000	8000	8000	2400*4= 9600
TOTAL samples*			2400*4= 9600		8000		

Type of sample		DBS for serology, collected at home**		nasal swab for PCR, collected at home**		
----------------	--	---------------------------------------	--	---	--	--

DBS = dried blood spot

1 Informed consent for household surveillance (by the household head) and sero-survey (by the selected individual or their caretaker) during baseline visit

2 During baseline visit adapted questionnaire to update population characteristics

3 Only of COVID-19 confirmed cases identified by the surveillance, at 28 and 56 days after symptom onset

4 We plan the social mixing survey rounds each time one month after the sero-survey, to spread the workload. The same participants from the sero-survey are asked to complete the questionnaire

\* estimated, based on the available information at the start of the study; we anticipate 8000 respiratory episodes (possible cases), based on previous data from the HDSS, adjusted for increased frequency of reporting (previous data was recorded during three-monthly rounds)

\*\* both serology testing of DBS and PCR testing of nasal swabs will be carried out at INS Marracuene. DBS samples are collected during pre planned visits, PCR samples when a possible case is identified. Nasal swabs undergo PCR testing the day following sample collection and results are communicated back to the individual (or his/her caretaker) that same day.

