All HDSS households will be visited by a trained HDSS interviewer to present the study and ask for informed consent (i) by the household head for the population-based surveillance and (ii) by the individuals selected for the age-stratified serial sero-survey. During this same visit, if the household head consented, the demographics data (baseline household visit form) will be verified and updated. A study household card with unique IDs of each household member will be provided (code containing the housing block, household id and sequential household member number). Household members will be sensitized on symptoms related to COVID-19, are asked to keep track of possible symptoms they may develop, and inform the study team by phone if a household member has a respiratory symptom, loss of smell or taste, so that upon assessment he/she can be asked to be swabbed for virological testing. In case a household member presents with symptoms which classify him/her as a possible case, a separate individual informed consent procedure for nasal swabbing will have to be performed prior to sampling. This ICF covers sampling for the first episode and any subsequent episode during the study period when nasal sampling would be indicated. Also during the baseline household visit, if full informed consent was provided (both for surveillance by the household head and for the sero- and social mixing survey by the individual household member), individual household members selected for the sero-survey will be asked for a baseline dried blood spot sample on filter paper, by administering a few blood drops through a finger prick.

Every two weeks a trained interviewer from the HDSS team will do calls to the head of the household or his representative, where during the call he will fill out a questionnaire (Household follow-up visit form) recording any respiratory symptoms, fever or other indicative sign of COVID-19 (at the time of the phone call, or in the last two weeks, if these symptoms go away), vaccination against COVID-19, and medical appointments that any family member has had.

Meanwhile (if applicable), demographic changes or changes in the chronic medical conditions of family members will be recorded. If a family member reports a respiratory sign or loss of smell or taste, with or without fever (possible case), a trained interviewer will do a home visit to this household.

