Household investigations will be held , whenever a household index case ) is identified, excluding households in which more than 3 household members (including the index case) are known to have tested positive for SARS-CoV-2 in the past 7 days. During household transmission investigation visits, all eligible household members will be proposed to self-administer a nasal swab if adolescent or adult, or a nasal swab will be collected by the interviewer if the participant is a child or unable to administer a nasal swab. A Dried blood spot sample will be collected. The household head will be requested to keep track of any clinical sign or symptom of household members during the month following the baseline visit, in a diary, and if so, notify the study team. For symptomatic household participants, study procedures of a possible case report, as detailed above, will be followed. 28 days after symptom onset of the household index case, again a nasal swab and DBS sample will be collected for each household member.

Table 3. Schedule of assessments and samples collected for household transmission investigations.

	Day0 Onset of symptoms of index case	Day X Diagnosis of index case	Day X+1 Sample collection from contacts	Day 28 28 days after onset of index
Index case		nasal swab	DBS	nasal swab + DBS
Household contacts			nasal swab + DBS	nasal swab + DBS

Collected swabs will be stored in viral transport media, kept on conditioned ice packs (0-8°C), then shipped twice a day to a fridge (2-8°C) in the CISPOC office, from where they will be dispatched for PCR-testing at INS in a cooled container (2-8°C) once a day.

Results of PCR testing will be reported once daily from the lab to the national COVID-19 surveillance (also coordinated by INS) and to the study team, who will within two hours inform the possible case on his/her (confirmed or negative) SARS-CoV-2 PCR result by phone and, if an infection is confirmed, provide instructions how to protect household members and when to seek specialized COVID-19 care at the Polana Caniço hospital (according to national guidance).

Confirmed cases will be followed up by phone 28 days and 56 days after symptom onset, to record clinical outcome, using the 'Confirmed case follow-up form'. If not possible to connect by phone, this will be filled in during the subsequent household visit, or through follow-up with the COVID-19 clinical management centre at Polana Caniço General Hospital (if the patient died or is still hospitalised).

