We will derive brand-specific total vaccine effectiveness against infection and against disease, in respectively a case-cohort design and a cohort design. Total vaccine effectiveness is the protection of vaccinees due to direct effects and added protection of vaccinees owing to vaccination of their neighbors or contacts, while overall vaccine effectiveness considers protection of an entire population, irrespective of the vaccination status of its individual members, due to the combination of total protection and protection of non-vaccinees due to vaccination of their neighbors or contacts (Ali et al 2015). To derive total vaccine effectiveness against infection, we will compare the proportion of sero-survey participants who seroconverted in the past 3 months among vaccinated against the proportion in non-vaccinated, adjusting for age and sex and other confounders. To derive total vaccine effectiveness against disease, we will compare the odds of vaccination among symptomatic confirmed SARS-CoV-2 cases detected through the population-based surveillance with the odds of vaccination among sero-survey participants who did not seroconvert in the past 3 months, in a case-cohort design. We will also explore overall vaccine effectiveness against disease using regression models comparing housing blocks with different levels of vaccination coverage among sero-survey participants.

We will estimate the conventional data-based secondary attack rate, which is the proportion of seroconversion among identified household contacts. However, these are not necessarily all secondary infections from the household index case, and could be tertiary. Therefore we will also derive a model-based secondary attack rate, estimating the number of actual secondary infections of the household index case. To do so, we could use a chain-binomial statistical model, as described by Jing et al (doi:10.1016/S1473-3099(20)30471-0), with an expectation-maximisation algorithm to account for (a) uncertainty in the infection time of asymptomatic infections, for (b) an incubation and infectious period distribution, as described in literature, and consider (c) the timing of symptom onset in

symptomatic household contacts and (d) the age-specific proportion of asymptomatic infections as estimated from the active population-based surveillance and sero-survey.

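### The data-based household secondary attack rate counts only seroconversions, in practice those between Day X+1 and Day 28; it leaves out other infected contacts, keeps previously immune ones in the denominator, and so is biased modestly downward

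*Combined protocol and SAP*

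**What the plan says.** Section 7.1 offers two household rates. The data-based one is given in the words "which is the proportion of seroconversion among identified household contacts". The other is model-based and is meant to separate infections caused by the index case from tertiary ones.

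The sampling is set out in section 5.1 and Table 3. Contacts give a nasal swab and a dried blood spot the day after the index diagnosis (Day X+1). Then, "28 days after symptom onset of the household index case, again a nasal swab and DBS sample will be collected for each household member". Section 4.2 adds: "Respiratory samples will be analysed by RT-PCR for SARS-CoV-2 to assess presence of virus and viral load". Contacts who develop symptoms are also swabbed under the surveillance procedures.

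Section 4.3 admits participants whatever their infection history. The only exclusion specific to household investigations is at household level: more than 3 members, index included, known positive in the past 7 days.

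Section 2 lists the household secondary infection rate as a primary objective, though Table 1 does not mark it in bold.

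**The concern.** The definition uses one of the two tests done on every contact and gives no rule for serostatus at the first sample. Three groups are affected.

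- **Early converters.** A contact infected in this household episode and already seropositive on Day X+1 cannot seroconvert afterwards and is scored as uninfected.
- **PCR-positive non-converters.** A contact with virus detected but no conversion by Day 28 is scored as uninfected.
- **Previously immune contacts.** They stay in the denominator although they are not, or are less, at risk.

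Each lowers the rate relative to the risk among susceptible contacts. More households do not reduce the error. It also varies with how late the index case is diagnosed, so comparisons between households or epidemic phases are affected. Table 1 lists risk factors for household infection as an outcome, and section 7.1 gives no other rule for who counts as an infected contact.

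**Working it through.** **The plan's sample size.** Inputs from section 7.2: p = 0.17, limit d = 0.05, design effect 3. The HDSS population is 15,393 (section 4.1). A 95% level is assumed, as the sentence does not state it.

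n = 3 × N·p(1−p) / [(d²/1.96²)(N−1) + p(1−p)] = 641.4, rounded up to 642.

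This reproduces the plan's 642. Without the finite population correction it is 650.4. The sample size is not in question.

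**Timing of the first contact sample.** Section 4.2 asks about symptoms in the last week. Section 5.1 asks about symptoms at the call "or in the last two weeks, if these symptoms go away". On laboratory timing: "Nasal swabs undergo PCR testing the day following sample collection". Contacts are sampled one day after confirmation.

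- Swab on the day of onset: 0 + 1 + 1 = Day 2.
- One-week look-back: 7 + 1 + 1 = Day 9.
- Two-week look-back: 14 + 1 + 1 = Day 16.

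The gap to Day 28 is therefore 12 to 26 days. Section 1.1 cites "a longer estimated serial interval of 3.96 days", so a typical secondary case has onset near Day 4. That is about 5 days before a Day 9 sample and 12 days before a Day 16 sample. The documents give no time to seroconversion, so the share already seropositive cannot be derived from them.

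**Size of the bias.** Let s be the share of contacts previously immune and x the share of infected contacts missed (early converters plus PCR-positive non-converters). The 17% is read as the risk among susceptible contacts.

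Observed rate = 0.17 × (1 − s) × (1 − x)

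For s = 3.8%, section 1.2 reports that a city survey in August 2020 "found an overall seroprevalence of 3.8% in Mauto city". The 10% row and all values of x above 0 are assumptions.

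| s | x = 0 | x = 10% | x = 20% |
|---|---|---|---|
| 3.8% | 16.4% | 14.7% | 13.1% |
| 10% | 15.3% | 13.8% | 12.2% |

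A full 5-point shift, to 12%, needs x = 1 − 0.12/0.1635 = 27% at s = 3.8%, or 1 − 0.12/0.153 = 22% at s = 10%.

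**Offset in the other direction.** A contact infected outside the household between the samples counts as an event. If the plan's 40% annual attack rate were spread evenly, the risk h would be 0.40 × 12/365 = 0.013 to 0.40 × 26/365 = 0.028. The 14.7% would become 0.962 × (0.153 + 0.83h) = 15.8% to 17.0%. This overstates the offset because the 40% includes household infections, but an epidemic is not even over the year. The amount is best treated as unknown.

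**What the proposed rule gives.** Take 600 contacts (Table 1), s = 3.8%, and 10% of infected contacts converting before Day X+1.

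- Previously immune: 22.8. Infected: 0.17 × 577.2 = 98.1. Early converters: 9.8.
- Plan's rule: (98.1 − 9.8)/600 = 14.7%.
- Proposed main figure, early converters all PCR-positive on Day X+1: 98.1/577.2 = 17.0%.
- Proposed main figure, early converters all PCR-negative and so removed: 88.3/567.4 = 15.6%.
- Sensitivity analysis, all seropositive PCR-negative contacts counted as infected: (88.3 + 32.6)/600 = 20.2%.

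At s = 10% the last two become 82.6/530.8 = 15.6% and 151.8/600 = 25.3%.

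**The case against.** **The window is inferred.** Section 7.1 names neither sample day. That is correct; the window follows from Table 3. About 16% of residents (2400/15,393) may have an earlier sero-survey sample, but no rule says it would serve as baseline. If seroconversion were instead read loosely as being seropositive on Day 28, prior immunity would count as infection: 3.8% + 0.962 × 17% = 20.2%. Either way a written rule is needed.

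**The model-based rate covers it.** A reader might infer that this rate is optional. It is not: section 7.1 commits to it, and only the choice of model is left open. But its stated purpose is to separate tertiary infections, and its listed inputs include neither contact PCR nor first-sample serostatus. The list may not be exhaustive, so this shows that the plan does not state a remedy, not that the modellers would ignore those data.

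**Delays are limited.** Patients are asked to phone when symptoms start, and households with more than 3 known positives are excluded. Both help. Even so, an eligible household may contain two contacts already known to be positive. Day 16 rests on the two-week look-back in section 5.1, which conflicts with the one week in section 4.2, so it is not an established figure.

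**The size is mostly assumed.** This stands. The only shift from documented inputs is 17% to 16.4%. A reader might put the plan's 40% attack rate in as prior immunity and obtain 10.2%. The documents do not support that, because 40% is an end-of-study figure and Table 1 takes the first 100 households.

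**Vaccination.** A reader might infer that vaccine-induced antibodies will inflate the rate. The documents give no rollout speed. The assay in section 5.4.2 measures both spike and nucleocapsid and is not said to call spike alone positive. A short classification rule is enough.

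**The denominator is a choice of estimand.** This is also fair. The plan does not say that its 17% applies to susceptible contacts only, so the population should be stated.

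**Conclusion.** The point holds as a modest, systematic downward bias with an inexpensive remedy. The shift is 0.6 points from prior immunity of 3.8% alone, and 2.3 to 3.9 points if 10-20% of infected contacts are also missed. Those figures rest on a true 17% among susceptible contacts and on an assumed missed share. They lie inside the planned 5 points, and community-acquired infection offsets them in part by an unknown amount.

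A reader might infer that the household estimate is unusable or its sample size wrong. Neither follows: the 642 reproduces, and the samples needed for a better rule are already scheduled. The definition should be changed because it sets aside PCR results held on every contact for a primary objective, and because the error depends on diagnosis delay.

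**What to change.** In section 7.1, replace the definition with the following.

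1. **Numerator.** Count a contact as infected if PCR-positive at the Day X+1, symptomatic or Day 28 swab, or if seroconverted between the two blood spots.
2. **Denominator, main figure.** Include contacts who were PCR-positive or seronegative on Day X+1; that is, remove those seropositive and PCR-negative on that day.
3. **Sensitivity analysis A.** Keep the removed contacts and count them as secondary infections.
4. **Sensitivity analysis B.** Remove contacts PCR-positive at baseline whose symptom onset was on or before the index case's onset (possible co-primary cases). If these are 5-10% of infected contacts (assumption), 17% becomes 93.2/572.3 = 16.3% to 88.3/567.4 = 15.6%.
5. **Vaccinated between samples.** When the vaccine contains no nucleocapsid, do not count a spike-only response without PCR positivity as infection. The data are planned (section 4.2): "Data will be collected on household exposures of contacts and vaccine receipt".

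**Cost.** Wording and two sensitivity analyses, with no new samples and no change in eligibility. The half-width is 1.96 × √(3 × 0.17 × 0.83/n): 5.2 points at n = 600, 5.3 at 577 (3.8% removed) and 5.5 at 540 (10% removed). Early converters who are PCR-negative on Day X+1 are still lost from the main figure. The bracket between the main figure and analysis A may be wide: 15.6% to 20.2%, or to 25.3% with 10% previously immune, in the scenario worked above. That uncertainty exists under the present definition too, but is not shown.
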